14.6 Evaluation of Safety

Safety assessments will include physical examinations, vital signs (BP, HR, body temperature), standard clinical laboratory safety tests (haematology, biochemistry, urinalysis), 12-lead ECGs and monitoring of AEs pre- and post-treatment. Safety analysis will be based on the safety set for the double-blind phase and the OLAS for the open-label extension phase. Missing values will not be imputed.

Dosing duration and frequency will be summarised.

14.6.1 Vital Signs

Vital signs will be summarised for each treatment group by visit. Summary statistics will be provided for actual values and change from baseline, where the baseline value is the last value prior to dosing.

14.6.2 Clinical Laboratory Safety Tests

The results of clinical laboratory tests and change from baseline will be summarised for each treatment group by visit, where the baseline value is the last value prior to dosing. Values outside the normal ranges will be flagged and summarised.

14.6.3 ECGs

ECGs will be summarised for each treatment group by visit. Summary statistics will be provided for actual values (based on the mean of the triplicate readings for each subject) and change from baseline, where the baseline is defined as the mean of the values recorded at the screening (Visit 1) ECG.

14.6.4 Adverse Events

All AEs will be listed by system organ class (SOC) and preferred term (PT) classifications assigned to the event using the Medical Dictionary for Regulatory Activities (MedDRA) (Version 20.1 or higher). The number of AEs and number (and %) of subjects with AEs will be summarised by SOC and PT. In addition, AEs will be summarised by severity, relationship to treatment, time to onset (following the last dose of IMP prior to AE start date) and duration (offset).

Listings will be presented for SAEs and AEs leading to withdrawal.

14.7 Sample Size

A sample size of $n = 250$ per group (total $N = 1000$) provides 90% study power to reject the null hypotheses for all three primary endpoints when comparing a MED2005 dose to placebo, using a Bonferroni corrected type I error, adjusting for three dose versus placebo comparisons. The sample size calculations were performed using EAST 6.4 in the continuous endpoint two-sample multiple comparisons multiple endpoints platform using the assumptions described below.

It is assumed that MED2005 is slightly better than alprostadil [33]. For the higher two doses alprostadil saw an improvement compared to placebo for IIEF-EF of 3.2 and 3.1 (least squares [LS] mean changes), giving an average of 3.15, for SEP Question 2 of 9.6 and 11.3 (LS mean changes), giving an average of 10.65, and for SEP Question 3 of 13.4 and 8.7 (LS mean changes), giving an average of 11.05. In Study FM53 there was a better improvement in SEP Question 3 than SEP Question 2 so the sample size assumptions take this into account. PDE 5's also appear to find SEP Question 2 more difficult to improve compared to placebo than SEP Question 3. Compared with the alprostadil results therefore it is assumed that the difference of MED2005 minus placebo for IIEF-EF is 3.2, for SEP Question 2 is 11.5 and for SEP Question 3 is 12.

Estimates of standard deviations are based on FM53 and published results from other ED treatments and are assumed to be 5.6, 33 and 33 for IIEF-EF, SEP Question 2 and Question 3, respectively [33, 34]. The differences between MED2005 and placebo for each endpoint are assumed to follow a multivariate normal distribution with the following correlation matrix, based on observed data from study FM53.

	IIEF-EF	SEP Question 2	SEP Question 3
IIEF-EF	1	0.5	0.5
SEP Question 2	0.5	1	0.6
SEP Question 3	0.5	0.6	1

For the open-label extension phase it is planned to recruit a total of 450 male subjects in order to meet ICH requirements.

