7. STUDY OBJECTIVES

7.1 Primary Objective

- To demonstrate the efficacy of MED2005 versus placebo in male subjects clinically diagnosed with ED using the EF domain of the IIEF, the Sexual Encounter Profile (SEP) Question 2 and the SEP Question 3. The primary objective will be addressed by estimating the following estimand: difference between treatment policies (each MED2005 dose versus placebo) in all subjects who met the study inclusion/exclusion criteria and who were randomised and attempted intercourse post-randomisation at least once, assessed via the change compared to baseline in EF [IIEF-EF], the ability to achieve vaginal penetration [SEP Question 2] and the ability to have successful intercourse [SEP Question 3] over 12 weeks of treatment

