9. SELECTION AND WITHDRAWAL OF SUBJECTS

9.1 Number and Source of Subjects to be Studied

It is planned to randomise and treat 1000 male subjects clinically diagnosed with ED, along with their female partners, in the double-blind phase of the study. Additional subjects may be randomised if there are a substantial number of dropouts to ensure that sufficient data are available for analysis; this would be detailed in a protocol amendment. Subjects will be identified and recruited through volunteer databases, site/clinician recruitment and/or advertisements as necessary.

For the open-label extension phase, it is planned to include a total of 450 male subjects and their female partners.

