9.6.2 Criteria for Withdrawal from the Study

Subjects (and their female partners) are free to withdraw from the study at any time, without prejudice (withdrawal of consent).

Subjects may be withdrawn from the study at any time; however, once treatment has commenced, every attempt should be made to continue with the safety and IIEF and SEP questionnaires up to the end of the double-blind phase to ensure the safety of the subject and in order to address the primary efficacy objective of difference between treatment policies.

Reasons for withdrawing a subject from the study can include:

- Voluntary discontinuation by the subject and/or his female partner, who are free to discontinue participation in the study at any time
- Severe non-compliance to the protocol as judged by the PI and/or Sponsor
- Any other reason as judged by the PI

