14.5.2 Handling of Missing Values

Full details on the handling of missing values in analyses of all analysis sets, including rules applied to incomplete questionnaires and planned additional analyses, will be defined in the SAP. Only the main principles are given for the analyses on the FAS here.

Summary statistics will present the number of missing values and then will be based on non-missing values.

Any missing values in efficacy questionnaire data that occur during the treatment period and are then followed by observed data shall be treated as missing at random and imputed using a corresponding multiple imputation approach.

All subjects who are withdrawn from the study will be asked to continue with the IIEF and SEP questionnaires if possible. These data will be used as part of the analysis for estimating the treatment effect over 12 weeks, according to the randomised treatment policy.

There can be remaining missing values for the primary endpoints for subjects who leave the study and provide no further questionnaire data. For these subjects, missing values will be handled using a control-based multiple imputation approach. The imputation model for the missing observations in both the MED2005 and placebo (control) groups will be constructed from the control group only (missing not at random [MNAR]). This assumes that efficacy results post withdrawal, for subjects who withdraw, would have mirrored those seen in the placebo group and thus lose any potential MED2005 treatment benefit.

Additional estimands/tests of treatment effect, beyond the primary treatment policy estimand, may be addressed, including exploring other ways of handling missing values, such as fitting repeated measures mixed models.

Summary statistics will present the number of observed values and will then be based on the non-missing values for the open-label extension phase.

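### Does the stated 90% joint power fail because no dropout allowance is given and leavers are imputed from placebo?

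*Protocol*

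**What the plan says.** Section 14.7 states that 250 men per group (1000 in total) "provides 90% study power to reject the null hypotheses for all three primary endpoints when comparing a MED2005 dose to placebo", with a Bonferroni-corrected type I error for three dose comparisons. It assumes that "the difference of MED2005 minus placebo for IIEF-EF is 3.2, for SEP Question 2 is 11.5 and for SEP Question 3 is 12". The standard deviations are 5.6, 33 and 33. The correlations are 0.5 between IIEF-EF and each SEP question and 0.6 between the two SEP questions. The differences are set slightly above those of a comparator product, whose results are quoted "for SEP Question 2 of 9.6 and 11.3 (LS mean changes), giving an average of 10.65".

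No dropout rate appears. The synopsis plans to randomise and treat the same 250 per group. Section 9.1 adds: "Additional subjects may be randomised if there are a substantial number of dropouts to ensure that sufficient data are available for analysis", by protocol amendment.

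On missing data, section 14.5.2 covers men who leave and supply nothing further: "The imputation model for the missing observations in both the MED2005 and placebo (control) groups will be constructed from the control group only". The stated reason is that their results after withdrawal "would have mirrored those seen in the placebo group and thus lose any potential MED2005 treatment benefit". The same section leaves full details to the SAP. Section 9.6.2 tries to keep this group small: once treatment has started, "every attempt should be made to continue with the safety and IIEF and SEP questionnaires up to the end of the double-blind phase".

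**The concern.** Two things catch the eye in section 14.7.

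First, the number calculated and the number to be randomised are the same, with nothing added for leavers. Under placebo-based imputation a leaver stays in the analysis but adds no treatment benefit after leaving, so the expected difference shrinks. Section 14.7 does not say whether 3.2, 11.5 and 12 are already net of that. If they are not, the 90% describes complete data and the primary treatment-policy analysis has less. All three endpoints must succeed, so a modest loss on the weaker ones would lower the chance of a positive result for a dose.

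Second, one of the three comparator averages is wrong as printed. An arithmetic error in a sample-size section raises the question of whether it fed into the calculation.

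**Working it through.** **Inputs.** From section 14.7: n = 250 per group; differences 3.2, 11.5 and 12; SDs 5.6, 33 and 33; correlations 0.5, 0.5 and 0.6. From section 14.5.3: two-sided 5% after multiplying p-values by three, so alpha = 0.05/3 and the critical value is z = 2.394; efficacy requires all three null hypotheses to be rejected.

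**Reproducing the 90%.** The standard error of each difference is SD × √(2/250), and the marginal power is Φ(difference/SE − 2.394).

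| Endpoint | SE | Difference/SE | Marginal power |
|---|---|---|---|
| IIEF-EF | 0.501 | 6.389 | >99.9% |
| SEP Question 2 | 2.952 | 3.896 | 93.3% |
| SEP Question 3 | 2.952 | 4.066 | 95.3% |

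The trivariate normal probability that all three succeed, with the stated correlations, is 90.4%. A simulation using t-tests gives 90.2%. At 247 per group joint power is 89.98%, and at 248 it is 90.12%. The protocol's 90% is correct.

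**Effect of dilution.** Let f be the share of the assumed difference lost to placebo-based imputation, with n kept at 250 because imputed men remain in the analysis. The values of f are assumptions; the protocol gives none.

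| f | All three endpoints | SEP Questions 2 and 3 only | IIEF-EF only |
|---|---|---|---|
| 2% | 88.9% | 88.9% | 90.4% |
| 5% | 86.3% | 86.3% | 90.4% |
| 10% | 81.2% | 81.2% | 90.4% |
| 20% | 67.8% | 67.8% | 90.3% |

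The loss comes almost entirely through the SEP questions. IIEF-EF has so much power that diluting it alone by a fifth hardly matters.

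**Possible offset.** The primary model is an ANCOVA with baseline and site, plus ED severity for SEP (section 14.5.3). Section 14.7 does not say whether the SDs are before or after covariate adjustment. If they are unadjusted and covariates explain 10% of variance (an assumption), each SD is multiplied by √0.90. Joint power is then 90.5% at f = 5% and 86.2% at f = 10%. If covariates explain 20%, it is 94.1% and 90.8%.

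**The averages.**
- IIEF-EF: (3.2 + 3.1)/2 = 3.15, as printed.
- SEP Question 3: (13.4 + 8.7)/2 = 11.05, as printed.
- SEP Question 2: (9.6 + 11.3)/2 = 10.45, printed as 10.65.

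Either the average or one input is misprinted: 10.0 with 11.3, or 9.6 with 11.7, would give 10.65. The power calculation uses 11.5, so the 90.4% above does not depend on which it is. The step from the comparator to 11.5 is 1.05 points from 10.45 and 0.85 points from 10.65.

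**The case for a change.** The strongest case for a change is that sections 14.5.2 and 14.7 are both fixed in this protocol and are not connected. One prescribes an imputation that removes benefit from leavers by design; the other quotes a power figure without saying whether that has been allowed for. Joint power falls below 90.0% once about 0.6% of the effect is lost on all endpoints, so even a small group of leavers matters. The option in section 9.1 has no rate, trigger or size and needs an amendment, so it is a contingency and not an allowance.

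Part of this stands. Section 14.7 would be clearer if it gave the basis of its differences and SDs, and a reader cannot settle the question from the text. Four things keep it from being an error.

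- The 0.6% threshold tests a rounded planning figure to a precision the protocol never claimed. Any sample size solved for 90% lies close to 90%.
- f is not the leaver rate. Withdrawn men are asked to go on completing IIEF and SEP. The SEP endpoints are percentages of attempts over the 12 weeks, so a man who leaves after some treated attempts already has data towards them. How far SEP values would be imputed at all is among the details left to the SAP.
- The assumed differences may already be net of leavers. They are benchmarked on between-group least-squares mean changes from a regulatory evaluation of another product, and the protocol does not say how dropouts were treated there.
- Loss of numbers as such does not arise. The full analysis set is every randomised man who used medication at least once (section 14.1), and missing primary values are multiply imputed.

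**Conclusion.** No change to the plan follows. The stated 90% is correct on the printed inputs (90.4%), and a margin of two men per group is ordinary for a size solved to that target. A shortfall is possible but conditional. It requires that the assumed differences are not already net of leavers, that an appreciable share of the effect is lost on SEP Questions 2 and 3, and that covariate adjustment does not make it good. On the first two conditions alone, with the same share lost on both SEP questions, power would be 88.9% at 2%, 86.3% at 5% and 81.2% at 10%. The protocol supports none of these shares in particular. Stating the basis of the differences and SDs would be a courtesy to the reader and would correct no figure.

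The SEP Question 2 average is a genuine slip (10.45 against 10.65), but a clerical one. It affects only the narrative comparison with the other product and alters no sample size, power figure, analysis or conclusion. It can be checked against its source whenever section 14.7 is next edited.

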15. DATA MANAGEMENT

The data management process is described below and subject to change after finalisation of the study roles and responsibilities which will be described in detail in the Data Handling Plan (DHP).

The CRO's Data Management department will be responsible for developing and maintaining the DHP; setting-up and validating the clinical study database; programming validation checks; entering data into the clinical study database; reviewing data for accuracy, completeness and consistency between the eCRFs and the database; and verifying adherence to the clinical pharmacology study protocol and the DHP. The study database will be built using appropriate software based on the eCRF design. Data entry will be performed using a double independent data entry method with second pass verification.

Clinical laboratory safety data will be loaded into the database as an electronic data transfer file according to the validated transfer specification document. Clinical data queries will be

generated and resolved according to the DHP. Clinical data queries will be resolved with the assistance of CRO and site clinical staff.

The study will involve two database locks. For the data up to and including Visit 6, after all clinical data queries are resolved, the final error rate is confirmed and QC checks are considered acceptable, the database will be locked. The same process will apply at the end of the open-label extension phase. Standard SAS® datasets will be generated from the final study database ready for the analyses. A complete audit trail of all corrections will be available for inspection.

AEs, diagnoses from Medical History and procedures from Surgical History will be classified according to the current version of MedDRA (Version 20.1 or higher). Previous and Concomitant Medications will be coded using the current version of the WHODrug dictionary (Version 1 March 2017 or higher). SAEs in the clinical database will be reconciled with the safety database.

15.1 Case Report Forms

eCRFs, paper diaries (for the collection of AEs and concomitant medications) and ePRO devices will be used to record the data in the study.

The Study Monitor will check data at the monitoring visits to the study sites. The PI will ensure that the data in the eCRFs are accurate, complete and legible.

Any missing, impossible (inconsistent with human life) or inconsistent recordings in the eCRFs will be referred back to the PI and documented for each individual subject before clean file status is declared.

16. SPONSOR AND INVESTIGATOR RESPONSIBILITIES

This study will be conducted in accordance with current applicable regulations, ICH, EU Directive 2001/20/EC and local ethical and legal requirements.

16.1 Sponsor Responsibilities

16.1.1 GCP Compliance

FMD and any third party to whom aspects of the study management or monitoring have been delegated will undertake their roles for this study in compliance with all applicable regulations and ICH GCP Guidelines.

FMD assigns the ICH compliance statement for the study to the CRO and ensures that the CRO complies with ICH GCP through a program of oversight activities including, but not limited to, review of project meeting minutes, attending initiation visits, and review of monitoring reports, etc.

Visits to the sites will be conducted to inspect study data, subject medical records and eCRFs in accordance with current GCP and the respective local and national government regulations and guidelines. Records and data may additionally be reviewed by auditors or by Regulatory Authorities.

16.1.2 Regulatory Approval

FMD will ensure that local Regulatory Authority requirements are met before the start of the study. FMD (or a nominated delegate) will be responsible for the preparation, submission and

confirmation of receipt of any Regulatory Authority approvals required prior to study commencement.

16.1.3 Indemnity/liability and Insurance

FMD will adhere to the recommendations of the Association of British Pharmaceutical Industry (ABPI) Guidelines. A copy of the indemnity document will be supplied to the CRO before study initiation.

FMD will ensure that suitable insurance cover is in place prior to the start of the study. An insurance certificate will be supplied to the sites.

16.1.4 Protocol Management

All protocols and amendments will be prepared by FMD and/or the CRO. If it becomes necessary to issue a protocol amendment during the course of the study, FMD will notify the CRO and collect documented Investigator Agreements to the amendment.

16.1.5 End of Study Notification

FMD (or a nominated delegate) will submit an end of study notification to the Competent Regulatory Authority of the Member State within 90 days of the end of the study, in accordance with EU Directive 2001/20/EC and to the local Regulatory Authority according to applicable regulatory requirements. FMD will forward copies of the end of study notification documents to the CRO. The CRO or their delegate will be responsible for submitting these to the relevant EC within 90 days of the end of the study.

16.1.6 Submission of Summary of Clinical Trial Report to Competent Regulatory Authorities of Member States Concerned and ECs

FMD will provide a summary of the clinical trial report within 1 year of the end of the study to the Competent Regulatory Authority of the Member States concerned, as required by the regulatory requirement and to comply with the community guideline on GCP. FMD will provide the PI with a copy of the summary report to forward to the relevant EC.

16.2 Investigator Responsibilities

16.2.1 GCP Compliance

The PI will have been assigned by FMD to perform the study in accordance with ICH GCP Guidelines, EU Directive 2001/20/EC and the applicable regulatory requirements and local regulatory requirements.

It is the PI's responsibility to ensure that adequate time and appropriate resources are available at the individual study sites prior to commitment to participate in this study. The PI should also be able to estimate or demonstrate a potential for recruiting the required number of suitable subjects within the agreed recruitment period.

The PI will maintain a list of appropriately Qualified Persons (QPs) to whom the PI has delegated significant study-related tasks. Up-to-date copies of the *curriculum vitae* for the PI, Co-Investigator(s) and essential study staff will be provided to FMD (or their delegate) before starting the study.

Agreement with the final clinical study report (CSR) will be documented by a dated signature of the PI, in compliance with Directive 75/318/EC, Directive 2001/83/EC and ICH E3 and local regulatory requirements.

16.2.2 Protocol Adherence and Investigator Agreement

The PI must adhere to the protocol as detailed in this document. The PI will be responsible for enrolling only those subjects who have met protocol eligibility criteria. The PI will be required to sign an Investigator Agreement to confirm acceptance and willingness for themselves and the Co-Investigator(s) to comply with the study protocol.

16.2.3 Documentation and Retention of Records

After completion of the study, all data and documents relating to the study will be kept in a secure and orderly manner by the CRO or their delegate in a secure file in an electronic or paper TMF. The data will be available for inspection by FMD or their representatives. Unless other union law requires archiving for a longer period, the Sponsor and the CRO shall archive the content of the TMF for at least 25 years after the end of the study. However, the medical files of subjects shall be archived in accordance with national law. The CRO or their delegate must contact FMD before destroying any study-related documentation and it is the responsibility of FMD to inform the investigative sites of when these documents can be destroyed.

16.3 Ethical Considerations

This protocol complies with the principles of the World Medical Assembly (Helsinki 1964) and subsequent amendments.

16.3.1 Informed Consent

It is the responsibility of the PI to obtain written informed consent from all subjects and their female partners to enter the study and also to obtain written informed consent from all subjects and their female partners to continue into the open-label extension phase. All consent documentation must be in accordance with applicable regulations and GCP. Each subject and his partner is required to sign the subject and partner ICF after they have both read the written subject information and received an explanation of what the study involves. This can include, but is not limited to: the objectives, potential benefits and risks, inconveniences and the subject's/partner's rights and responsibilities. Signed consent forms must remain on file and must be available for verification by Study Monitors at any time. A signed original copy of the informed consent documentation (ICF or Subject Information and ICF, as applicable) must be given to the subject and his partner or the subject's/partner's legally authorised representative.

The CRO will provide the Sponsor with a copy of the EC approved consent forms, and a copy of the EC written approval, prior to the start of the study. Additionally, if the EC required modification of the sample Subject Information and ICF documents provided by the Sponsor, the documentation supporting this requirement must be provided to the Sponsor.

